The goal of this proposal is to establish proof-of-principle and provide evidence that the EC and EC-HC communication are affected positively by aerobic exercise, and that those seniors with a smaller EC volume relative to brain size and those who perform more poorly on behavioral tests of EC function, will benefit most strongly. Interaction between the EC and the HC memory system is vital for allocentric spatial navigation and context-dependent memory formation. Critically, loss of function of the EC is a central factor in the pathophysiology of AD. Apparently healthy older adults show impaired allocentric navigation compared to young adults (Moffat et al., 2002; Moffat et al., 2009). Spatial navigation deficits may distinguish those at risk of developing AD from normal cognitive aging (Lithfous et al., 2013). We hypothesize that the EC and EC-hippocampal functional connectivity are important functional/anatomical targets of aerobic exercise. In this study, we will examine whether the EC and other MTL areas and EC-hippocampal functional connectivity are responsive to aerobic exercise. We will also investigate whether particular subsets of participants, such as those with poor performance on tests of spatial cognition or those with greater EC atrophy, might be more responsive to aerobic exercise.

Behavioral and fMRI Pilot Studies

The purpose of the pilot studies is to develop the cognitive tasks for fMRI and adapt them for our aging sample. For fMRI we do not generally use existing, normed, tasks such as those neuropsychologists would use. Instead, we develop cognitive tasks such that they are optimized to answer our specific research question outlined above for Aims #1 and #2. The pilot studies will be optimized for the specific population studied (healthy older adults) while at the same time taking into account technical constraints of fMRI (e.g. low temporal resolution, responses most often restricted to button presses).

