We propose to examine the effects of exercise and cardiovascular fitness on cognitive processes utilizing a parallel design randomized clinical trial. Specifically, we will investigate if exercise improves brain function in a brain area known as the entorhinal cortex. Together with the hippocampus this brain area is important for memory formation and spatial navigation. Participation in this research study will take approximately 4 months. During this time, participants will make three initial study visits. The first visit is for informed consent and screening, the second visit is for baseline fitness testing, and the third visit is for cognitive testing and a functional MRI exam. Functional MRI is a brain imaging technique that uses a magnetic field to "take pictures" of the brain while a person performs a cognitive task. It will take up to approximately three weeks to complete these initial three study visits. Following the three initial study visits, the exercise-training program will begin. Participants will be randomized to one of two training

programs: a cardiovascular endurance-training program (aerobic exercise) and a strength, balance, and flexibility training program (non-aerobic exercise). The exercise training program will last 12 weeks. There will be three one-hour exercise sessions per week. After completion of the exercise-training program, participants will attend two follow-up study visits. The first follow-up visit is for fitness testing. The second follow-up visit is for cognitive testing and an MRI exam.

Design and Procedures

Participants will be randomized into one of two groups: 1) an aerobic exercise intervention group and 2) a non-aerobic exercise control group (strength, balance, flexibility training). They will have a 50% chance to be randomized into one of the two groups.

The PI will be responsible for the randomization, because the PI's role in participant recruitment and screening is minimal. The study staff members performing the recruiting, informed consent, and screening will not know which group each participant will be randomized to at the time of recruitment, informed consent, or screening.

1) Study Visit 1: Informed Consent and Screening

Duration of Study Visit 1: Approximately 2 hours. These numbers include informed consent, general screening, breaks and neuropsychological testing. The duration of the neuropsychological testing is approx. 60-80 minutes (including breaks).

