s/he may be asked to make decisions about the presented stimuli, scenes, or environments, and to indicate responses on handheld response keys or with a joystick. Between each set of stimuli there will be a short break. We will remind the participant to keep his or her head as still as possible during task performance and the breaks in between.

We may take measurements of blood pressure, heart rate and/or pulse immediately before entering and immediately after exiting the fMRI scanner room. During fMRI scanning we may use pulse oximetry.

Outcomes

Describe anticipated primary outcome and any secondary outcomes and how they will be measured:

Primary Outcomes for Specific Aim #1:

1) Better cognitive task performance post-exercise training compared to baseline (measurements: reaction times, accuracy, etc.); effect expected to be greater for aerobic exercise training than control (strength, balance and flexibility training)

Measurements: reaction times, accuracy, and other cognitive task derived scores

2) Increased activation in and functional connectivity between brain areas associated with task performance, effect expected to be greater following aerobic exercise training than control. Measurements: blood-oxygen level dependent fMRI scans

Primary Outcomes for Specific Aim #2:

1) Better cognitive task performance post-exercise training compared to baseline (measurements: reaction times, accuracy, path length, spatial reasoning test scores, etc.); effect expected to be greater for aerobic exercise training than control (strength, balance, and flexibility training)

Measurements: reaction times, accuracy, path length, and other cognitive task derived scores

2) Increased activation in and functional connectivity between brain areas associated with task performance, effect expected to be greater for aerobic exercise training than control; this effect of aerobic exercise training will be greater for subjects with 1) smaller compared to larger relative entorhinal cortex volume, and 2) below-median compared to above median path integration skills

Measurements: blood-oxygen level dependent fMRI scans

Secondary outcomes for all aims:

1) Increased aerobic capacity for aerobic exercise group participants

Measurements: VO2max (estimated from submaximal incremental work rate test)

2) Increased strength for control group participants

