and compare them between and within groups with mixed-design ANOVAs. We will use baseline fitness as a covariate. Because the entorhinal cortex and the hippocampus are our primary brain regions of interest, we will use a seed-based functional connectivity approach. We will compare task-related functional connectivity: 1) pre versus post intervention, and 2) aerobic exercise versus control. We will use the psycho-physiological interaction (PPI) approach91 using the Generalized PPI Toolbox92 for SPM8. The time course from a seed region constitutes the physiological variable, and the contrast of interest (e.g. high memory load > low memory load) constitutes the psychological variable in the PPI model. Our search space will be restricted to the medial temporal lobe region. We will determine the PPI variable by calculating the voxel-wise product between the physiological and the psychological variables. We will also correlate SPMs and functional connectivity strength with cognitive test scores. Analyses will include nuisance regressors (e.g. head motion).

Specific Aim #2:

Data Analysis. See Aim #1. The behavioral outcome variables of the primary cognitive task (allocentric navigation task) are distance traveled and movement speed. Addicional outcome variables are neuropsychological test scores and spatial reasoning test scores. Analyses will be as described for Specific Aim #1. In addition, we will compare two groups that differ in relative EC volume or path integration ability (by median split) using descriptive statistics (means, confidence intervals) due to the exploratory nature/ small sample size.

Sample Size

Sample Size Justification

Approximately 94 participants will be recruited total for the study: For the exercise training program

/study intervention, approximately 84 participants will be recruited with the aim to enroll 42 participants, 21 per group; for the cognitive and fMRI pilot studies, an additional 10 participants will be recruited with the aim to enroll 5 participants in the cognitive pilot and 5 participants in the fMRI pilot. Thus, this totals 94 participants (84 + 5 + 5 = 94) required to complete the cognitive pilot, fMRI pilot, and exercise training program/study intervention.

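### Aim 2 examines two continuous moderators by median split; an arm-by-continuous-moderator estimate would use the 42 participants better if the effect is roughly linear, though it would still be imprecise

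*Combined protocol and SAP*

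**What the plan says.** All references are to the combined protocol and SAP.

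- **Data Analysis, Specific Aim #2.** After referring back to the Aim 1 methods, the plan adds that "we will compare two groups that differ in relative EC volume or path integration ability (by median split) using descriptive statistics". The output is limited to "means, confidence intervals) due to the exploratory nature/ small sample size". The text does not say whether exercise arm enters this comparison.
- **Outcomes, Primary Outcomes for Specific Aim #2, item 2 (activation and connectivity).** The hypotheses are that "this effect of aerobic exercise training will be greater for subjects with 1) smaller compared to larger relative entorhinal cortex volume", and likewise for "below-median compared to above median path integration skills".
- **Goal of the proposal (opening section).** The study is to give evidence that "those seniors with a smaller EC volume relative to brain size and those who perform more poorly on behavioral tests of EC function" gain the most. The background just before it says that response may depend on how far the entorhinal cortex (EC) has atrophied or lost function.
- **Sample Size Justification and Design and Procedures.** Recruitment is "with the aim to enroll 42 participants, 21 per group", allocated 1:1 ("They will have a 50% chance to be randomized into one of the two groups"). No power or precision figure is given for the moderator comparison.

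The only other continuous analysis correlates activation maps and connectivity with cognitive scores. That does not address whether the effect of aerobic training varies with a baseline moderator.

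**The concern.** A relative volume and a task score are continuous by nature (the documents do not say so in terms). Cutting either at the sample median treats two people just either side of the cut as opposites, and everyone within a half as identical. The cut-point depends on who happens to enrol, so the resulting contrast does not carry over directly to another study.

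The plan gives the small sample as a reason for the descriptive split. A small sample is a good reason to avoid formal claims, but it argues against discarding information about the moderator. What is at stake is the precision with which a stated goal of the study can be described.

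**Working it through.** **The plan's own figure.** The documents size the cognitive group-by-time comparison at 32 in total (f = 0.26, power 0.80, alpha 0.05), raised to 42. For a 2 × 2 repeated-measures interaction, λ = f²·N·m/(1−ρ). With m = 2 and ρ = 0.5 (assumed; no correlation is stated), λ = 0.0676 × 32 × 2 / 0.5 = 8.65. On 1 and 30 df this gives power 0.812, and 32 is the smallest even N to reach 0.80. The figure reproduces, but it does not concern the moderators.

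**Information kept by a median split.** For a linear moderator effect, the fraction kept is the squared correlation between the moderator and its above/below-median indicator.

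- Normal moderator: 2/π = 0.637, a loss of 36.3%.
- Equivalent sample: 42 × 0.637 = 26.7 people. Conversely, 42/0.637 = 66 people would be needed under the split to match 42 analysed continuously.
- Standard error of the standardised slope: larger by √(1/0.637) = 1.25.

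The documents give no distribution for either moderator, so the range matters:

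| Assumed moderator distribution | Loss from split (linear effect) |
|---|---|
| Uniform, or well-separated bimodal | 25% |
| Normal | 36% |
| Gamma (shape 4) | 41% |
| t with 5 df | 46% |
| Lognormal (sigma 0.5) | 48% |
| Laplace | 50% |
| Exponential | 52% |

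**Interval width, both analyses on one scale.** This step assumes that the halves are compared by arm, which the plan does not state. Two arms of 21 cut at the pooled median give on average 42/4 = 10.5 per cell. The unit is the residual SD of change, with 42 − 4 = 38 df and t = 2.024.

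- Split: SE of the difference in treatment effect between halves = √(4/10.5) = 0.617; 95% CI half-width 2.024 × 0.617 = **1.25 SD**.
- Continuous, normal moderator: SE of the difference in slopes between arms is about 2/√42 = 0.309 per moderator SD. The means of the two halves lie 2√(2/π) = 1.60 moderator SDs apart. Half-width 2.024 × 0.309 × 1.60 = **1.00 SD**.

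**Illustrative power.** No test is planned and the documents state no slope, so these figures only show the direction. They come from simulation with N = 42, a normal moderator, a linear effect and two-sided 0.05; slopes are the arm difference in SD of change per moderator SD.

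| Assumed slope | Continuous | Median split |
|---|---|---|
| 0.5 | about 32% | about 22% |
| 0.8 | about 66% | about 46% |
| 0.9 | 76% | 56% |

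With a slope of zero, both analyses reject about 5% of the time.

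**If the true effect is a step at the median.** With a step coefficient of 0.9 (the treatment effect differs by 1.8 SD between halves), the split has 80% power and the linear model 58%. The advantage reverses.

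**The case against.** The strongest reply has four parts.

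1. **The comparison is labelled exploratory and descriptive.** This stands: the cost is a wider interval, and no powered test fails. But a descriptive interval is exactly where lost precision shows, and the continuous estimate can be just as exploratory. That the same hypotheses sit under primary outcomes is a separate question of status, which the two sections should reconcile.
2. **The hypotheses are worded by group.** The Outcomes section does contrast smaller with larger and below with above the median. The background's reference to degree of atrophy suggests grading but does not establish it. A reader might infer that the documents commit to a graded effect; they do not. Equally, they propose no threshold, and nothing in them suggests a step at the sample median.
3. **The loss is not a fixed figure.** A reader might infer that the split necessarily discards over a third of the information. That needs a normal moderator and a linear effect, and the documents supply neither. The loss is smaller for flat or bimodal scores, larger for skewed or heavy-tailed ones, and absent if the effect is a step at the median.
4. **The missing arm term matters at least as much.** The plan speaks only of two groups. If arm is left out, the comparison cannot address whether the aerobic effect differs between halves, whatever form the moderator takes. The proposed regression brings arm in as well, so its whole benefit should not be credited to dropping the split. The loss from the split does remain once arm is included.

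**Conclusion.** The point holds in a conditional form. The median split is planned for both moderators and no arm-by-continuous-moderator model is specified. With a roughly normal moderator and a roughly linear effect, the split loses about 36% of the information on moderation (25% to 52% for the other distributions tried). If the halves are compared by arm, the interval is about ±1.25 SD instead of about ±1.0 SD.

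Two stronger readings are not supported. One is that the change would let the trial settle who benefits most: ±1.0 SD is still wide, and most of the imprecision comes from 42 participants and remains after the fix. The other is that the split undermines the trial's main result: the group-by-time comparison does not use it. This is a cheap improvement to an exploratory analysis. The direction is secure unless the moderation is step-like near the median; the exact size rests on assumptions that the documents do not settle.

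**What to change.** In Data Analysis, Specific Aim #2, replace the median-split comparison with one regression per moderator: change in the outcome on arm, the standardised continuous baseline moderator (relative EC volume, or path integration score) and their product. Report the product term with its 95% CI, labelled exploratory. Keep the median halves for plots only. State explicitly that arm is in the model.

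The cost is a change of analysis wording, with no new data, visits or participants. The downside is that the product term assumes a linear moderator effect. Check this on a scatterplot of change against the moderator by arm, and say so in the report if the pattern looks step-like.

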Measurements: upper body strength in lbs or kg (based on chest press and latissimus dorsi pulldown), lower body strength in lbs or kg (based on leg press)

3) Increased lean body mass

Measurements: Percent lean body mass from BIA (and/or skinfold measures)

4) Neuropsychological test performance: improved performance scores on tests of spatial cognition, verbal memory, visuo-spatial memory, visuo-spatial attention, and executive functions post-exercise training compared to baseline and compared to controls

Measurements: neuropsychological test scores

Data Analysis

Provide a description of your plan for data analysis. State the types of comparisons you plan (e.g. comparison of means, comparison of proportions, regressions, analysis of variance). Which is the PRIMARY comparison/analysis? How will the analyses proposed relate to the primary purposes of your study? If you are doing qualitative research please state how comparisons will be made.

Specific Aim #1:

Behavioral and Fitness Data Analysis. The primary measures for the primary cognitive task (Sternberg memory load task) are % correct and reaction times, and for fitness are estimated VO 2 max. The primary statistical analyses will be repeated-measures ANOVAs with the factors group (aerobic vs. control) and time (pre vs. post) to examine group x time interactions on the outcome measures. Posthoc tests (e.g. Tukey tests) will examine if a significant group x time interaction is due to a greater improvement post-intervention in the aerobic exercise group compared to controls. Dependent measures will be tested for normality and skewed data log-transformed. We will use an alpha of 0.05, corrected for multiple comparisons.

Univariate fMRI and Functional Connectivity Analyses. We will use SPM8 and related software for statistical analysis of fMRI data. We will estimate voxel-based Statistical Parametric Maps (SPMs)

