For the exercise training program/study intervention, the sample size for enrollment was determined from simulation-based power predictions for fMRI (Desmond & Glover, 2002), and based on a metaanalysis on exercise training effects on cognition in older adults (Colcombe and Kramer, 2003). 1) fMRI: Given an estimated mean difference of 0.5% signal change, a between-subject variance of 0.5%, and a statistical power of 0.80, a sample size of 11-12 subject per group would be needed for $\alpha = 0.05$ and N = 21 per group for $\alpha = 0.002$. 2) Cognition: we performed sample size calculations with G*Power 3.1.7 based on effect sizes reported in the literature. Effect sizes were f = 0.26 for a short-duration exercise intervention, f = 0.30 for session durations of 45 min, f = 0.20 for cardiovascular training only, f = 0.21 for the visuospatial domain, and f = 0.35 for participants aged 65+ years. Based on an average f of 0.26, a statistical power of 0.80, and alpha = 0.05, a total N = 32 subjects will be needed. Oversampling to 42

Risks and Benefits

Risks associated with the cardiovascular fitness and strength tests

The exercise test will require a gradual increase of exercise intensity. Because it is very strenuous to reach maximum oxygen uptake even after rest it may pose a health risk for some participants. Risks and discomforts include the possibility of adverse changes during the test, including abnormal blood pressure, fainting, dizziness, severe fatigue, body aches, heart rhythm abnormalities, stroke, and very rare instances of heart attack.

Risks and discomforts associated with the strength tests include feeling tired and experiencing muscle cramps. Other, less common, risks and discomforts include muscle tear, spraining a ligament (connective tissue) and lightheadedness.

Risks associated with bioelectrical impedance analysis (BIA)

The bioelectric impedance analysis (BIA) uses a very small electrical current, which passes between electrodes placed on the hands and/or feet. The amount of this current is slight enough that the participants will not be able to feel it and poses no risk to humans. However, there is a slight risk that this low current could disrupt an artificial pacemaker or defibrillator.

Risks associated with exercise

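### For aerobic versus control, the stated fMRI inputs do not yield 11-12 and 21 per group: with 0.5% read as an SD, 21 per group has about 48% power at two-sided alpha 0.002, not 80%

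*Combined protocol and SAP*

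**What the plan says.** The Sample Size Justification states that "the sample size for enrollment was determined from simulation-based power predictions for fMRI", together with a meta-analysis of exercise effects on cognition. The fMRI part begins "Given an estimated mean difference of 0.5% signal change, a between-subject variance of 0.5" per cent. The size for alpha 0.05 is then worded as "a statistical power of 0.80, a sample size of 11-12 subject per group would be needed for" that threshold. The stricter threshold follows in the same sentence, "and N = 21 per group for" alpha 0.002. Recruitment proceeds "with the aim to enroll 42 participants, 21 per group", so planned enrolment equals the alpha 0.002 figure.

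Under Outcomes, activation and connectivity are primary for both aims, and the increase is expected to be greater after aerobic training than after control. The Univariate fMRI and Functional Connectivity paragraph of Data Analysis says that the maps will be estimated "and compare them between and within groups with mixed-design ANOVAs", so both kinds of contrast are planned. It adds: "We will use baseline fitness as a covariate". No fMRI significance threshold is given. The only analysis alpha is in the Behavioral and Fitness paragraph: "We will use an alpha of 0.05, corrected for multiple comparisons".

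The sizing line does not state the contrast, the sidedness, whether 0.5% is a variance or an SD, whether it refers to one visit or to the pre-post change, or any pre-post correlation.

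**The concern.** A size per group, in a two-arm trial whose primary activation hypothesis is a between-arm one, will be read as the size for the between-arm test. On that reading the numbers looked too small: a standardised difference of 1.0 needs more than 11-12 per arm at alpha 0.05 and far more than 21 at alpha 0.002.

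What is at stake is how the result is interpreted. If a strict threshold is applied and the aerobic and control arms do not differ, the plan as written lets that null be presented as coming from a test with 80% power. The stated inputs do not show that.

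**Working it through.** **Inputs.** From the Sample Size Justification: difference 0.5% signal change, spread 0.5%, power 0.80, alpha 0.05 and 0.002, 21 per group. Assumed here because the plan is silent: t-tests, two-sided unless marked, and 0.5% first read as an SD, so d = 0.5/0.5 = 1.0. Read literally as a variance of 0.5, the SD is sqrt(0.5) = 0.707 and d = 0.707. Power comes from the noncentral t distribution. This checks the stated inputs; it does not reproduce the cited simulation.

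**Step 1: can the stated pair (11-12 and 21) be reproduced?** Two routes come close.

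- *One group, one-sample or paired.* Noncentrality = d × sqrt(n), df = n − 1. With d = 1.0, 0.80 power needs n = 10 at alpha 0.05 and n = 21 at alpha 0.002 (power 0.826 at 21, 0.792 at 20). This matches 21 but not 11-12, and it requires 0.5% to be the SD of the pre-post change.
- *Between arms, on change scores.* SD of change = SD per visit × sqrt(2(1 − r)). With a per-visit SD of 0.5% and an assumed r = 0.70, this is 0.5 × sqrt(0.6) = 0.387, so d = 1.29. The test needs 11 and 21 per group. This matches both figures, but r is not in the documents.

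**Step 2: aerobic versus control on the stated inputs alone.** Two-sample test, noncentrality = d × sqrt(n/2), df = 2n − 2. At n = 21 and d = 1.0, noncentrality = sqrt(10.5) = 3.24 with df = 40. The two-sided critical value is 3.31 at alpha 0.002 and 2.02 at alpha 0.05.

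| Reading | n per group for 0.80 power (alpha 0.05 / 0.002) | Power at 21 per group (alpha 0.05 / 0.002) |
|---|---|---|
| SD 0.5%, two-sided | 17 / 34 | 0.885 / 0.483 |
| SD 0.5%, one-sided | 14 / 30 | 0.938 / 0.577 |
| Variance 0.5, two-sided | 33 / 65 | 0.609 / 0.175 |
| Variance 0.5, one-sided | 26 / 58 | 0.728 / 0.241 |

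With SD 0.5%, the stated 11 and 12 per group have two-sided power 0.607 and 0.649 at alpha 0.05 (0.732 and 0.767 one-sided). A Monte Carlo check (200,000 runs, n = 21, SD 0.5%, two-sided) gave 0.887 and 0.484 at alpha 0.05 and 0.002. The difference detectable with 80% power at 21 per group is 1.29 SD at alpha 0.002 and 0.89 SD at alpha 0.05.

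**Step 3: how far an unstated correlation moves the result.** Per-visit SD 0.5%, between-arm change scores, 21 per group, two-sided:

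| Assumed r | SD of change | Power, alpha 0.05 | Power, alpha 0.002 |
|---|---|---|---|
| 0.3 | 0.592 | 0.762 | 0.304 |
| 0.5 | 0.500 | 0.885 | 0.483 |
| 0.6 | 0.447 | 0.942 | 0.624 |
| 0.7 | 0.387 | 0.983 | 0.800 |

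If baseline activation were the covariate instead (residual SD = SD × sqrt(1 − r²), df = 39), r of about 0.63 would be enough at alpha 0.002. The covariate that the plan names is baseline fitness.

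**The case against.** The strongest reply is that the plan used simulation-based fMRI predictions, whose settings a closed-form test cannot recover. A simulation with a between-arm change-score design and a correlation near 0.70 would give just the sizes stated. That stands as a possibility, and it is why no error in the original simulation can be asserted. It does not make the line verifiable: no correlation or simulation setting is given, and at alpha 0.002 power falls to 0.62 at r = 0.6 and 0.48 at r = 0.5.

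A second reply is that the line never says that 0.80 at alpha 0.002 applies to aerobic versus control. That is true. But it gives sizes per group, enrolment equals one of them, and the primary activation hypothesis compares the arms. If another contrast was meant, the line should say so.

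A third is that little depends on alpha 0.002. It appears nowhere in the analysis plan. At uncorrected two-sided alpha 0.05 with SD 0.5% there is no shortfall, and at 0.05/2 power is still 0.815 (0.767 at 0.05/3). Enrolment also has a cognition basis: N = 32, then raised to 42. All of this stands and limits the reach of the point.

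Three stronger readings are tempting but unsupported:

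- *That 21 was computed for a within-group contrast and misapplied.* The one-sample test gives 10, not 11-12, at alpha 0.05, needs its own unstated reading of the 0.5%, and fits the pair no better than the change-score route.
- *That the trial is too small and needs 34 per group.* This would require alpha 0.002 to be the analysis threshold and SD 0.5% to apply to the analysed scale. The plan states neither.
- *That connectivity is underpowered too.* The inputs are in per cent signal change and say nothing about connectivity measures.

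**Conclusion.** The point holds in a limited form. For the between-arm activation comparison, the stated inputs do not produce 11-12 and 21 per group under any of the four plain two-sample readings (SD or variance, one- or two-sided). At 21 per group and alpha 0.002, power is 48.3% two-sided if 0.5% is an SD, and between 17.5% and 57.7% across the four readings, against an implied 80%. At uncorrected two-sided alpha 0.05 it is 88.5% with SD 0.5%, but 60.9% if 0.5 is a variance.

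These figures assume t-tests and no variance reduction beyond what the plan states. A pre-post correlation of about 0.70 with a per-visit SD of 0.5% would restore 80%, so the defect is a size unsupported by its own stated inputs; no faulty simulation has been shown. It should be fixed, because the line underlies enrolment and bears on a primary outcome of both aims. Confidence is moderate.

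**What to change.** Keep 42 participants and restate the fMRI activation line of the Sample Size Justification. It should give:

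- the contrast to which 21 per group refers;
- whether 0.5% is an SD or a variance, and of one visit or of the change;
- the test and its sidedness;
- the pre-post correlation or other simulation inputs, with their justification;
- the alpha that governs the between-arm test.

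If no such input can be stated and justified, remove the implied 0.80 power at alpha 0.002 for aerobic versus control. Possible replacement: *For aerobic versus control, conditional on a standardised difference of 1.0 on the analysed scale, 21 per group gives 88.5% power at two-sided alpha 0.05 and about 48% at two-sided alpha 0.002; the difference detectable with 80% power at alpha 0.002 is about 1.29 SD.* If 0.5% is a per-visit SD, add the range at alpha 0.002: 30%, 48%, 62% and 80% for assumed r = 0.3, 0.5, 0.6 and 0.7. Do not apply these figures to the connectivity outcomes.

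The cost is wording only, with no change in enrolment. The downside is that the stated between-arm power at alpha 0.002 becomes less favourable, unless the sponsor can document the input that supports 21.
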